##### **2.2.1.2.2 Secondary efficacy variables for subjects entering Part B**

- Time to flare

- ASDAS disease activity (ASDAS-ID, ASDAS-LD, ASDAS-HD, and ASDAS-vHD) and clinical improvement (ASDAS-CII, ASDAS-MI) at Week 96
- Assessment of SpondyloArthritis International Society (ASAS) response criteria ASAS20, ASAS40, ASAS5/6, and ASAS partial remission (PR) response at Week 96
- Change from Part A Baseline in ASDAS, Bath Ankylosing Spondylitis Disease Activity Index (BASDAI), Bath Ankylosing Spondylitis Functional Index (BASFI), and Bath Ankylosing Spondylitis Metrology Index (BASMI) at Week 96
- BASDAI50 response at Week 96
- Change from Part A Baseline in Sacroiliac Joint (SIJ) Sacroiliac SpondyloArthritis Research Consortium of Canada (SPARCC) and spine ankylosing spondylitis spine MRI score for activity (ASspiMRI-a) in the Berlin modification scores at Week 96

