### **8.2.2.2 Continuous secondary efficacy variables**

Summary statistics of observed and change from Part B Baseline to Week 96 values for ASDAS, BASDAI, BASFI, and BASMI will be presented by treatment group. These summary statistics will be repeated for Part A Baseline.

The changes from Part B Baseline to Week 96 in ASDAS, BASDAI, BASFI and BASMI will be compared between treatment groups using a MMRM. The pattern of missingness for these variables is assumed to be MAR. Post-flare data for subjects experiencing a flare (in any treatment group) will be treated as missing in the MMRM analysis. The MMRM methods will be applied to all observed change from Part B Baseline data obtained from Week 48 up to Week 96. The model will include Part B Baseline score as a fixed-effect covariate, treatment group, region, mNY classification, and visit as fixed-effect categorical factors, and Part B Baseline-by-visit and treatment group-by-visit as interaction terms. The multiple visits for each subject will be incorporated as repeated measures (fixed term) within each subject (random term). An unstructured covariance matrix will be used and visit will be treated as a categorical predictor. An unstructured correlation pattern will be used to estimate the variance-covariance of the within-subject repeated measures. Summary tables will present the adjusted means for PBO and the CZP doses, the respective differences to PBO, the corresponding p-values, and 95% CIs.

The comparison between treatment groups using MMRM will be repeated for Part A Baseline with Part A Baseline score as a fixed-effect covariate, treatment group, region, mNY classification, and visit as fixed-effect categorical factors, and Part A Baseline-by-visit and treatment group-by-visit as interaction terms.

Summary statistics of observed and change from Part B Baseline to Week 96 values for SIJ SPARCC and Spine ASspiMRI-a in the Berlin modification scores will be presented by treatment group. These summaries will be based on observed case data.

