The changes from Part B Baseline in SIJ SPARCC and spine ASspiMRI-a in the Berlin modification scores at Week 96 will be compared between treatment groups using an analysis of covariance (ANCOVA) model. The model will include Part B Baseline score, treatment group, region, and mNY classification. Summary tables will present the adjusted means for PBO and the CZP doses, the respective differences to PBO, the corresponding p-values, and 95% CIs. This analysis will be performed using observed case data only.

These summary statistics will be repeated for Part A Baseline and the model includes Part A Baseline score, treatment group, region, and mNY classification.

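### The Week 96 change-from-Part-A-Baseline endpoints are analysed without adjusting for the score at randomization, so one arm contrast gets two nominal results

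*SAP*

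**What the plan says.** SAP section 2.2.1.2.2 lists the Week 96 secondary variables for Part B. The entry for the clinical scores begins "Change from Part A Baseline in ASDAS, Bath Ankylosing Spondylitis Disease Activity Index (BASDAI), Bath Ankylosing Spondylitis Functional Index (BASFI" and goes on to BASMI. The MRI entry begins "Change from Part A Baseline in Sacroiliac Joint (SIJ) Sacroiliac SpondyloArthritis Research Consortium of Canada (SPARCC" and adds the spine score. Both use Part A Baseline as reference. Change from Part B Baseline in these scores appears in section 2.2.1.3.2, among the other efficacy variables.

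Section 8.2.2.2 takes the two in the opposite order. It first states: "The changes from Part B Baseline to Week 96 in ASDAS, BASDAI, BASFI and BASMI will be compared between treatment groups using a MMRM". For that analysis, "The model will include Part B Baseline score as a fixed-effect covariate", together with its interaction with visit. The response visits are given as follows: "The MMRM methods will be applied to all observed change from Part B Baseline data obtained from Week 48 up to Week 96". Then comes the Part A version: "The comparison between treatment groups using MMRM will be repeated for Part A Baseline with Part A Baseline score as a fixed-effect covariate". The MRI ANCOVA follows the same pattern; in its Part A version, "the model includes Part A Baseline score, treatment group, region, and mNY classification".

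Section 3.4 defines Part B Baseline as the last measurement on or before the day of randomization. Neither Part A model includes it as a covariate. Sections 4.5 and 8.2.2 put all secondary p-values outside the fixed testing sequence and call them nominal.

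**The concern.** For subjects in Part B, the Part A Baseline score was taken about 48 weeks before randomization, before any open-label treatment. The Part B Baseline score is the value at the moment the arms diverge, and would normally be expected to predict Week 96 better. The model for the declared endpoint leaves that value out, so a chance imbalance in it between arms stays uncorrected and the residual variance is larger than it need be.

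The two versions also look like answers to two questions, but for the comparison between arms they are not. The report will carry two estimates, two intervals and two p-values for the same Week 96 difference, for each score and each dose. Nothing in the SAP says which of them is the analysis of the variable in section 2.2.1.2.2. At stake are the precision and clarity of the declared secondary endpoints.

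**Working it through.** **Inputs.** From the SAP: 70 subjects per arm and two-sided 0.05 (section 2.4); covariates as in section 8.2.2.2. The SAP states no power, SD, effect size or correlation for these endpoints, so there is no figure of its own to reproduce here. (Section 2.4's power for the flare endpoint, 98% and 94%, is reproduced to within about 1 point by Fisher's exact test, at 98.9% and 94.0%, but does not bear on this point.) Assumed for illustration: SD 1, true difference 0.4 SD, complete data, two-arm ANCOVA, correlation between the two baselines 0.3. The correlations with Week 96 are varied: r_A for Part A Baseline and r_B for Part B Baseline.

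**Step 1: same contrast.** Let Y be the Week 96 score, A and B the two baselines, T the arm. If Y − A = a + τT + βA, then Y = a + τT + (β + 1)A. The arm coefficient for change adjusted for its own baseline is therefore that for the Week 96 level adjusted for that baseline. The same holds with B. A numerical check gave agreement to about 4 × 10⁻¹⁶. Under randomization both versions target the arm difference in Week 96 score and differ only in the covariate.

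**Step 2: precision.** SE ≈ √[(2/70)(1 − r²)], with √(2/70) = 0.169, so the ratio of SEs is √[(1 − r_A²)/(1 − r_B²)]. The last column is from 4,000 simulated trials per row.

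| r_A | r_B | SE, Part A model | SE, Part B model | SE ratio | p-values on opposite sides of 0.05 |
|---|---|---|---|---|---|
| 0.3 | 0.3 | 0.161 | 0.161 | 1.00 | 11% |
| 0.1 | 0.3 | 0.168 | 0.161 | 1.04 | 9% |
| 0.2 | 0.5 | 0.166 | 0.147 | 1.13 | 16% |
| 0.3 | 0.7 | 0.162 | 0.121 | 1.34 | 25% |

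Two further pairs by the same formula: (0.1, 0.4) gives √(0.99/0.84) = 1.09, and (0.3, 0.6) gives √(0.91/0.64) = 1.19. In the simulation the mean estimates from the two models agreed within 0.001 SD, so neither is biased.

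**Step 3: both baselines together.** If Y − A = a + τT + β₁A + β₂B, then Y − B = (Y − A) + (A − B) = a + τT + (β₁ + 1)A + (β₂ − 1)B. Only the baseline coefficients change; τ, its SE and its p-value are identical. In simulations with correlation 0.2 between the baselines, the SE with both covariates was 0.156, 0.146 and 0.132 for (r_A, r_B) = (0.1, 0.4), (0.2, 0.5) and (0.3, 0.6). With B alone it was 0.155, 0.147 and 0.135; with A alone, 0.168, 0.166 and 0.161.

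**Step 4: Week 48 as a response.** Section 8.2.2.2 has responses start at Week 48. Where Part B Baseline is the Week 48 score, change from Part A Baseline at Week 48 is B − A, and change from Part B Baseline is 0. With both baselines as covariates the Week 48 response is fully determined and cannot stay in the MMRM.

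**The case against.** The strongest reply is that the declared endpoint is analysed, with a full model, and that adjusting a change score for its own baseline is conventional. This stands. A reader might infer from the order of the paragraphs that the SAP contradicts section 2.2.1.2.2, or has replaced the declared endpoint by the Part B version. The text does not support that: no sentence in 8.2.2.2 ranks one version above the other, and change from Part B Baseline is a declared variable too.

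Second, a reader might take disagreement across 0.05 as a threat to the trial's conclusions. It is not one: the p-values are nominal, and both results will be reported under their labels.

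Third, the size rests on assumption. It would go too far to say that the plan throws away a fixed share of its subjects; with equal correlations there is no loss of precision. For ASDAS, section 3.2.21 requires a score below 1.3 at Week 48 and section 3.2.7 gives a minimum of 0.636. Part B Baseline then spans at most 0.664 units and its SD is at most 0.332. The SE of a chance arm difference is at most 0.332 × 0.169 = 0.056 units. That is small, and a restricted range tends to lower the correlation with Week 96. The bound does not extend to the other scores.

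Fourth, four of the six scores are analysed by MMRM with post-flare data set to missing. With section 2.4's no-flare rates of 80% and 45%, only about 56 full-dose and 32 placebo subjects would reach Week 96 without a flare, so complete-data figures at 70 per arm do not describe that model. If Week 48 stays a response in the Part A repeat, the value at randomization also enters there. With complete data and treatment-by-visit terms this does not adjust the Week 96 contrast, but under missing-at-random data it would inform incomplete cases.

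**Conclusion.** The point holds as one of efficiency and consistency. The model for the declared Week 96 endpoints omits the score at randomization as a covariate, and the plan will report two nominal results for one arm difference without saying which answers section 2.2.1.2.2. The MRI ANCOVA is the plainest case, since it has no repeated responses through which the Week 48 score could enter.

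Under the assumed correlations the SE penalty on the Part A version is none when the two baselines predict Week 96 equally well. It is 4–13% at intermediate values, and 19–34% when the Part A correlation is 0.3 and the Part B correlation 0.3–0.4 higher. The ASDAS penalty may be smaller, and the MMRM figures will differ. Both versions are unbiased with complete data. The primary conclusion and its type I error do not change.

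**What to change.** In section 8.2.2.2, include both the Part A and the Part B Baseline score in the models for both change scores: each with its by-visit interaction in the MMRM, and as two covariates in the MRI ANCOVA. Use only visits after Week 48 as responses. State that the resulting single contrast is the analysis of the section 2.2.1.2.2 variables. Fitted to the same subjects and visits, the two change scores then give the same arm difference, interval and p-value, while the descriptive summaries from each baseline can stay as they are. Section 8.3.2.3 carries the same pair of models by visit, and the sections that refer to it would follow.

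The cost is SAP wording, a covariate already collected, and a few more parameters to estimate. The real downside is that subjects missing either baseline drop out of the comparison. This matters mainly for the observed-case MRI ANCOVA, where a missing Screening or Week 48 scan would exclude a subject from both versions; the number lost should be reported.

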### **8.2.2.3 Binary secondary efficacy variables**

The number and percentage of subjects in the ASDAS disease activity levels (ASDAS-ID, ASDAS-LD, ASDAS-HD, ASDAS-vHD) as well as the number and percentage of subjects achieving ASDAS clinical improvement (ASDAS-CII, ASDAS-MI), ASAS response (ASAS20, ASAS40, ASAS5/6, ASAS PR) and BASDAI50 response will be summarized at Week 96 by treatment group. These summaries will be based on observed case data and will be repeated using NRI data (for all variables except ASDAS disease activity level); improvement will be relative to Part A Baseline only.

The statistical analysis of ASDAS clinical improvement (ASDAS-CII, ASDAS-MI), ASAS response (ASAS20, ASAS40, ASAS5/6, ASAS PR) and BASDAI50 response at Week 96 will

be based on a logistic regression model which will include factors of treatment group, region, and mNY classification. The responder rates for each treatment group and the adjusted odds ratios with reference to PBO will be estimated from this logistic regression model and presented with 95% 2-sided CIs and p-values. This analysis will be performed using NRI data.

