### **2.4       Determination of sample size**

It is anticipated that approximately 210 subjects will be randomized in a 1:1:1 ratio to the CZP 200mg Q2W, CZP 200mg Q4W, and PBO treatment groups. The primary efficacy analysis is based on the proportion of subjects who do not experience a flare during Part B of the study. The proportion of subjects who do not experience a flare during Part B is assumed to be 80%, 75%, and 45% for the CZP 200mg Q2W, CZP 200mg Q4W, and PBO treatment groups, respectively. Given these assumptions, a sample size of 70 subjects per group provides 98% power to detect a significant difference between the CZP 200mg Q2W dose and PBO and 94% power to detect a significant difference between the CZP 200mg Q4W dose and PBO using a 2-sided significance level of 0.05.

Given that subjects enter Part B only if they have achieved sustained remission in Part A, it is necessary to estimate the number of subjects needed to enroll in Part A. It is assumed that approximately 28% of subjects enrolled in Part A will achieve sustained remission and qualify for Part B. This means that about 750 subjects will be enrolled in Part A in order to have 210 subjects who are randomized into Part B.

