The study design has three different periods: Part A, Part B and Escape Part. The outputs will be presented for each period. Summaries for Part A will be presented by axSpA subpopulation. Summaries for Part B will be presented by treatment group excluding any post-flare assessments in the subset of subjects experiencing a flare in Part B and start escape therapy. For the subset of subjects experiencing a flare in Part B and start escape therapy, separate summaries will be produced for the Escape Part.

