### **3.2.4 MRI assessments**

Magnetic resonance imaging of the spine and sacroiliac joints will be performed at Screening, Week 48, Week 96, or Withdrawal Visit if the previous MRI was performed more than 12 weeks prior to withdrawal. In the Escape Part it will be also performed at Escape Week 0 and 12. MRI will be assessed centrally and scoring will be done according to the imaging charter by independent readers, who are blinded to both the order of the scans and to the treatment group,

using a previously reported scoring system. A single reader assessment will be performed for Week 0 and Week 48 in the MRI scores for all subjects that entered Part A and have at least one post-baseline scan. A double reader assessment will be performed for subjects entering Part B. The analysis will use the average of the scores from the 2 independent reviewers. If the two readers disagree a third reviewer who is not one of the two reviewers will perform adjudication by providing a third independent review. Whenever an adjudication is present the average score across all 3 reviewers will be used for analysis. Two different MRI scores will be used for analysis (SPARCC, Berlin modification of the ASspiMRI-a).

The SPARCC scoring method for lesions found on the MRI is based on an abnormal increased signal on the short-tau-inversion recovery (STIR) sequence, representing bone marrow edema (defined as an increased signal in bone marrow on a T2-weighted sequence, reflecting an increased concentration of “free water” related to a bone lesion). Each SIJ is divided into 4 quadrants and will be assessed for left and right: upper iliac, lower iliac, upper sacral, and lower sacral. The presence of increased signal on STIR in each of these 4 quadrants are scored on a dichotomous basis, where 1 = increased signal and 0 = normal signal. Joints that include a lesion exhibiting intense signal are each given an additional score of 1 per slice that demonstrated this feature. Similarly, each joint that included a lesion demonstrating continuous increased signal of depth greater or equal 1 cm from the articular surface is also given an additional score of 1. The scoring is repeated in each of 6 consecutive coronal slices. Total SIJ SPARCC scores can range from 0 to 72.

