### **4.2 Handling of dropouts or missing data**

Post-flare efficacy data (except radiographic data) for subjects experiencing a flare (in any treatment group) will be treated as missing in Part B analyses. The pattern of missingness for these variables is assumed to be missing at random (MAR). For the summaries of data collected at post-flare visits in subjects experiencing a flare, there will be no adjustment for missing values and only observed case descriptive summaries will be provided.

For the primary efficacy variable (percentage of subjects in Part B who do not experience a flare), an approach based on the principles of NRI will be used to impute missing values. Specifically, if a subject withdraws from Part B at any point, they will be considered as having not responded to treatment. Therefore, they will be assumed to have experienced a flare during Part B for analysis purposes. Sensitivity analyses will be performed to assess the robustness of the results obtained using the NRI approach. Refer to Section 3.2.22 of this SAP for further details.

For the time to flare endpoint, the rules as described above for the primary endpoint will be applied to account for missing data when determining whether or not a subject experienced a

flare. Similarly, sensitivity analyses will also be performed to assess the robustness of the results obtained using the NRI approach. Refer to Section 3.2.23 of this SAP for further details.

For all analyses of binary endpoints (sustained remission, ASDAS-MI, ASDAS-CII, modified ASDAS-MI, ASAS20, ASAS40, ASAS5/6, ASAS PR, BASDAI50 response, IBD-Q remission, IBD-Q response, SF-36 PCS response, SF-36 MCS response) NRI will be used. Thus, unless mentioned otherwise (see Section 3.2.2 for ASAS20, ASAS40, ASAS5/6 and ASAS PR), a subject having missing data for the time point assessed will be conservatively counted as a non-responder. This will be done whether the data is missing, the subject discontinued prior to the time point assessed, or the data is considered missing due to start of escape treatment. For the following continuous endpoints in Part A, imputation of missing data will be performed using the LOCF approach:

- ASDAS
- BASDAI
- Fatigue item of BASDAI
- BASFI
- BASMI
- Nocturnal spinal pain score
- PtGADA
- CRP

In addition, ASDAS disease activity levels (ASDAS-ID, ASDAS-LD, ASDAS-HD and ASDAS-vHD) will be imputed based on the imputed values of ASDAS.

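### The Week 96 ASDAS activity-state table has no NRI repeat, so subjects who flared and escaped drop out of it, and the SAP does not settle which scans enter the Week 96 MRI ANCOVA

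*SAP*

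**What the plan says.** SAP 2.2.1.2.2 lists the ASDAS activity states (ID, LD, HD, vHD) at Week 96 among the Part B secondary variables. On their handling, 8.2.2.3 states: "These summaries will be based on observed case data and will be repeated using NRI data (for all variables except ASDAS disease activity level". They are the only variable in that section without the NRI repeat. They are also absent from the list of binary endpoints given NRI in 4.2, and they get no logistic model. Section 8.3.2.12 summarises them by visit, again as observed cases.

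On data after flare, 4.2 states: "Post-flare efficacy data (except radiographic data) for subjects experiencing a flare (in any treatment group) will be treated as missing in Part B analyses". Section 3.1 states: "Summaries for Part B will be presented by treatment group excluding any post-flare assessments in the subset of subjects experiencing a flare in Part B"; it adds that these are subjects who start escape therapy, and it makes no exception for imaging.

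For the Week 96 MRI scores, 8.2.2.2 specifies an ANCOVA with p-values and adds: "This analysis will be performed using observed case data only". On the extra scans in flared subjects, 3.2.4 says: "In the Escape Part it will be also performed at Escape Week 0 and 12".

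**The concern.** Part B asks what happens when treatment is withdrawn or reduced in subjects who were in remission. ASDAS-ID at Week 96 is a direct measure of whether remission was kept. Flare is defined on the same score: at least 2.1 at two consecutive visits, or above 3.5 once (3.2.22). Once a flared subject starts escape treatment, later values no longer count. The table meant to show high and very high disease activity therefore loses most of the subjects who reached it, and it loses more of them on placebo than on active treatment.

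No other rule fills the gap. The sentence in 4.2 that derives activity levels from imputed ASDAS belongs to the Part A LOCF list, and 3.10 removes LOCF from the Part B efficacy tables.

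For MRI the difficulty is different. Two general rules point in opposite directions, and the ANCOVA section does not say which one applies. Two programmers could build different datasets, and the choice could be made after unblinding.

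**Working it through.** **Inputs.** SAP 2.4 gives non-flare rates "assumed to be 80%, 75%, and 45% for the CZP 200mg Q2W, CZP 200mg Q4W, and PBO treatment groups, respectively". It also says that "a sample size of 70 subjects per group provides 98% power to detect a significant difference between the CZP 200mg Q2W dose and PBO". For half dose against placebo the stated figure is 94%, again two-sided at 0.05. The SAP gives no rate for the ASDAS states and no MRI effect. Below, q is an assumed share of ASDAS-ID among non-flared subjects: q1 on full dose, q2 on placebo.

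**The plan's own figure.** Power = Φ[(d − 1.96·se0)/se1], with se0 = √(2p̄(1−p̄)/70) and se1 = √([p1(1−p1)+p2(1−p2)]/70).
- 80% vs 45%: (0.35 − 1.96×0.0818)/0.0763 = 2.485, giving 99.4%; 98.9% with a continuity correction of 1/70.
- 75% vs 45%: (0.30 − 1.96×0.0828)/0.0788 = 1.747, giving 96.0%; 94.1% with the correction.

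Both lie within 2 points of the stated 98% and 94%, so the planning rates are used as they stand.

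**Who remains at Week 96.** Placebo 70×0.45 = 31.5; half dose 70×0.75 = 52.5; full dose 70×0.80 = 56. These counts are approximate. A subject who first meets the flare rule at Week 96 keeps that value, and a non-flared subject with a missing Week 96 value drops out.

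**ASDAS-ID, full dose minus placebo.** With flares counted as not inactive the difference is 0.80·q1 − 0.45·q2. As observed case it is q1 − q2. The loss is 0.55·q2 − 0.20·q1.

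| q1 / q2 (assumed) | Flares counted | Observed case | Points lost |
|---|---|---|---|
| 0.80 / 0.80 | 64 − 36 = 28 | 0 | 28 |
| 0.85 / 0.75 | 68 − 34 = 34 | 10 | 24 |
| 0.85 / 0.65 | 68 − 29 = 39 | 20 | 19 |
| 0.90 / 0.60 | 72 − 27 = 45 | 30 | 15 |

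The contrast shrinks whenever q2 exceeds (0.20/0.55)·q1 = 0.36·q1, so the direction is robust and the size is not.

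**Simulated ASDAS paths.** These are illustrative and calibrated to 20%, 25% and 55% flare. A share of subjects lose control and ramp over 8 weeks to a mean ASDAS of 2.6; visit noise has SD 0.3; the flare rule is that of 3.2.22. The contrast below is between placebo and full dose, in points.

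| Loss of control | State | Last pre-escape value used | Observed case |
|---|---|---|---|
| Early (mean 10 weeks) | HD+vHD | 57 vs 21: 37 | 7 vs 1: 5 |
| Early | ID | 28 vs 62: 34 | 62 vs 77: 16 |
| Even over 48 weeks | HD+vHD | 63 vs 23: 40 | 27 vs 6: 21 |
| Even over 48 weeks | ID | 18 vs 59: 41 | 35 vs 71: 36 |

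(Differences are taken before rounding.) With early loss most of the HD+vHD contrast and about half of the ID contrast go. With evenly spread loss about half of the HD+vHD contrast goes, but only about 5 points of ID.

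**MRI, passages side by side.** Under 3.1, Part B summaries omit assessments after flare and escape, so the ANCOVA would compare non-flared subjects only. Under 4.2, if radiographic data includes MRI, post-flare scans stay in. Section 2.3.3 moves flared placebo and half-dose subjects to full dose for at least 12 weeks, so their Week 96 scans would follow that treatment. Flared full-dose subjects stay on their allocation. If a flare adds D to the score and escape reverses a share r in every arm, the flare-driven contrast falls from (0.55 − 0.20)·D = 0.35·D to (1 − r)·0.35·D. The SAP gives neither D nor r, so the effect cannot be sized.

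**The case against.** The case for leaving the plan alone is substantial. The ASDAS states are only described, so no test is biased, and the MRI p-values are nominal (8.2.2). The withdrawal effect is reported elsewhere with flare or escape as failure: the primary endpoint, time to flare, and the ASDAS-CII, ASDAS-MI, ASAS and BASDAI50 analyses. Section 3.3 places the last pre-escape visit of flared subjects in a Last/Withdrawal Visit summary where applicable. Section 3.1 also allows a missing category, and with a Randomized Set denominator that would by itself lower the ASDAS-ID percentages. NRI has no natural non-responder level across four states. Keeping post-escape scans by randomised arm may be a deliberate treatment-policy choice. The Escape Week 0 scan falls at varying times, and 3.2.4 accepts it up to 2 weeks after that visit, possibly after the first escape dose.

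Most of this limits the point without removing it. The Last/Withdrawal summary does not feed the Week 96 table or the ANCOVA. Section 3.1 offers the missing category only as one of two options, so the percentage base stays open. The lack of a non-responder level is met by a separate category. The timing objection to the Escape Week 0 scan stands, and it rules that scan out as the main ANCOVA value.

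A reader might infer that the remaining groups are alike by construction and the withdrawal effect erased. The documents do not support this: the flare rule does not separate ASDAS-ID from ASDAS-LD, and the tables in the working show contrasts surviving. A reader might also infer that the MRI comparison uses re-treated subjects. That holds only if radiographic includes MRI, and then only for placebo and half dose. Nor can the share of placebo scanned after escape be read from the 55% flare rate, because 3.2.22 counts premature withdrawals as flares.

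**Conclusion.** The point holds as a gap in a descriptive secondary table and an unresolved conflict over MRI. At Week 96 the ASDAS-state table conditions on not having flared and escaped, which at planned rates removes about 38.5 of 70 placebo subjects and 14 of 70 on full dose. The ASDAS-ID contrast is attenuated by 15 to 28 points across the assumed rates, and by less if loss of control comes late. These sizes rest on assumed inactive-disease rates and simulated paths; the SAP supplies only the flare rates. For MRI the conclusion is only that the analysis dataset is not fixed. The primary analysis, its error control and the NRI-handled endpoints are not touched.

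**What to change.** **ASDAS states.** In 8.2.2.3 and 4.2, add a Week 96 state table with the full Randomized Set as denominator and a separate category for flared, escaped or missing, counted as not ASDAS-ID. Keep the observed-case table beside it. Analyse ASDAS-ID with the NRI logistic model already used for the other binary endpoints. At 64% vs 36% with 70 per arm that comparison has about 92% power: (0.28 − 1.96×0.0845)/0.0811 = 1.41.

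**MRI.** Before unblinding, reconcile 3.1 with 4.2: state whether radiographic includes MRI, and whether scans after escape enter the between-arm ANCOVA. Add a sensitivity analysis that uses the Escape Week 0 MRI for flared subjects, limited to scans before the first escape dose, and report its timing by arm.

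**Cost.** SAP wording, one extra table, one extra nominal model and one MRI sensitivity analysis. All the data are already collected. The drawback of the MRI sensitivity analysis is that its scan times vary and may differ by arm.
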